3.0 LIST OF ABBREVIATIONS

λ_z	terminal disposition phase rate constant
%CV	percent coefficient of variation
AE	adverse event
Ae_t	amount of drug excreted in urine from time 0 to time t
Ae_{t1-t2}	amount of drug excreted in urine from time 1 to time 2
ALT	alanine aminotransferase
AST	aspartate aminotransferase
AUC	area under the concentration-time curve
AUC_{24}	area under the concentration-time curve from time 0 to 24 hours
AUC_{∞}	area under the concentration-time curve from time 0 to infinity, calculated using the observed value of the last quantifiable concentration
AUC_{last}	area under the concentration-time curve from 0 to time of the last quantifiable concentration
BMI	body mass index
bpm	Beats per minute
BUN	blood urea nitrogen
$C_{\text{av,ss}}$	average concentration during a dosing interval, at steady state
CI	confidence interval
CL_R	renal clearance
C_{max}	maximum observed concentration
C_{min}	minimum observed concentration during a dosing interval
CPK	creatine phosphokinase
CRF	case report form
C_{trough}	observed concentration at the end of a dosing interval
ECG	electrocardiogram
FAS	full analysis set
f_{et}	fraction of administered dose of drug excreted in urine from time 0 to time t
GGT	γ -glutamyl transferase
HIV	human immunodeficiency virus
ICH	International Conference on Harmonisation
IVRS	Interactive Voice Response System
LDH	lactate dehydrogenase
LLN	lower limit of normal
LOCF	last observation carried forward
MedDRA	Medical Dictionary for Regulatory Activities
PD	pharmacodynamics
PK	pharmacokinetics
QOL	quality-of-life
PRO	patient-reported outcome
SAE	serious adverse event

SAP	statistical analysis plan
SDB	standard database
TLGs	tables, listings, and graphs
$t_{1/2z}$	terminal disposition phase half-life
t_{\max}	time of first occurrence of C_{\max}
ULN	upper limit of normal
V_z/F	apparent volume of distribution during the terminal disposition phase after extravascular administration, calculated using the observed value of the last quantifiable concentration
WHODrug	World Health Organization Drug Dictionary

4.0 OBJECTIVES

4.1 Primary Objectives

To assess the pharmacokinetics (PK) of TAK-491 40 mg and 80 mg in healthy Chinese subjects after both single and multiple dose administration.

4.2 Secondary Objectives

To evaluate the safety and tolerability of TAK-491 40 mg and 80 mg in healthy Chinese subjects after both single and multiple dose administration.

4.3 Additional Objectives

Not applicable.

4.4 Study Design

This is a randomized, open-label and double-blind, placebo-controlled, single- and multiple-dose, phase 1 study to evaluate the PK, and safety of TAK-491 or placebo as a single dose followed by multiple doses in healthy adult Chinese subjects.

Sixteen subjects will be randomized 1:1 to TAK-491 40 mg or 80 mg, eight subjects per each TAK-491 arm, in the open-label part of the study; the 2 regimens will be conducted in parallel as shown in [Table 4.a](#).

Table 4.a Open-Label Study Regimen and Subject Allocation

Regimen	Regimen Description	Number of Subjects
A	TAK-491 40 mg as a single dose followed by multiple doses	8
B	TAK-491 80 mg as a single dose followed by multiple doses	8

Forty-eight subjects will be randomized 1:1:1 to TAK-491 40 mg or 80 mg, or placebo, sixteen subjects per each arm, in the double-blind part of the study; the 3 regimens will be conducted in parallel as shown in [Table 4.b](#). To maintain the study blind, subjects in this part of the study will receive a least 1 placebo tablet; the TAK-491 40 mg and TAK-491 80 mg tablets differ in size; therefore, placebo tablets for each size will be utilized as appropriate.

Table 4.b Double-Blind Study Regimen and Subject Allocation

Regimen	Regimen Description	Number of Subjects
A	TAK-491 40 mg + placebo as a single dose followed by multiple doses	16
B	TAK-491 80 mg + placebo as a single dose followed by multiple doses	16
C	Placebo (2 tablets) as a single dose followed by multiple doses	16

The pre-dosing study period will consist of a Screening Period (Study Days -28 to -2) and Check-in (Study Day -1). On Day 1, a single dose of TAK-491 or placebo will be administered followed by a pharmacokinetic sampling period through 72 hours postdose (Days 1-4). On Days 4 through 10, subjects will be on a daily dosing regimen, followed by a 24-hour pharmacokinetic assessment period prior to Study Exit (Day 11). The total confinement period for a subject who completes the study will be 12 days. All subjects will return to the site for PK sampling on Days 12 to 13 and follow-up serum chemistry tests on Day 14. A Follow-up telephone call will be made by the site at 14 (± 2) days following the last dose of study medication (Day 24 ± 2 days) to inquire for any ongoing adverse events or serious adverse events (SAEs), new adverse events or SAEs, and concomitant medications taken since the final dose of study medication or Early Termination Visit.

A schematic of the study design is included as [Figure 4.a](#). A schedule of assessments is listed in [Table 4.c](#).

Figure 4.a Schematic of Study Design

Screening	Check-in	Dosing and PK	72-hr PK	Dosing (a)	Dosing and AM Trough Level (b)	Dosing and 24-hr PK	Study Exit	F/U Visit (c)	F/U Call
Days -28 to -2	Day -1	Day 1	Days 2-4	Day 4	Days 5-9	Day 10	Day 11	Day 14	Day 24 (± 2)

PK=pharmacokinetic.

(a) Dosing will occur after the collection of the 72-hr pharmacokinetic sample.

(b) PK Trough samples will be collected on Days 7 to 9.

(c) Serum chemistry testing.

Table 4.c Schedule of Study Procedures

Study Day	Screening	Check-in	Single and Multiple Dose							Study Exit (o)	PK collection	F/U Visit	ET Visit (a)	F/U Phone Call (b)
	Days -28 to -2	Day -1	Day 1	Days 2-3	Day 4	Days 5-6	Days 7-9	Day 10	Day 11	Days 12-13	Day 14			
Informed consent (c)	X													
Inclusion/exclusion criteria	X	X												
Demographics and medical history	X													
Medication history	X													
Physical examination	X	X								X		X		
Vital signs (d)	X	X	X	X	X	X	X	X	X	X		X		
Weight, height and BMI (e)	X	X								X		X		
Concomitant medications (f)	X	X	X	X	X	X	X	X	X	X	X	X	X	X
Concurrent medical conditions (g)	X	X												
Clinical laboratory tests (h)	X	X			X					X		X	X	
Virology testing (i)	X													
Pregnancy test (hCG) (j)	X	X								X			X	
Urine drug and cotinine screens and breath alcohol	X	X												
12-lead ECG	X	X								X			X	
Study drug dosing (k)			X		X	X	X	X						
PK blood collection (l)				X	X	X		X	X	X	X			
PK urine collection (m)			X	X	X	X			X	X				
PTE assessment (n)	X	X	X											
AE assessment			X	X	X	X	X	X	X	X	X	X	X	X

Footnotes for Table 4.c are on the next page.

Footnotes for Table 4.c

ET=early termination.

(a) Conduct procedures for subjects discontinued early. The PK sample collection should not be collected at the Early Termination Visit if a PK sample is not scheduled. Additional procedures may be performed at the discretion of the investigator to assess safety.

(b) A Follow-up telephone call will be made by the site at 14 (± 2) days following the last dose of study medication (Day 24 ± 2) to inquire for any ongoing adverse events or serious adverse events (SAEs), new adverse events or SAEs, and concomitant medications taken since final dose of study medication or Early Termination Visit. Any spontaneously reported AEs will continue to be collected for 30 days after the last dose of study medication or Early Termination.

(c) ICF must be signed before any study specific procedures are performed.

(d) Sitting blood pressure, pulse, respiration rate and oral temperature will be measured on Day -1, and on confinement days, vitals are to be measured pre-dose or upon morning rising. Vitals will be collected prior to the PK blood collection.

(e) Height (for calculation of BMI) will only be measured at Screening. Weight will be measured at Screening, Check-in (Day -1), and Study Exit or Early Termination Visit.

(f) Record all ongoing medications.

(g) Concurrent conditions are medical conditions that are present at Screening (time of informed consent).

(h) Hematology, serum chemistries, and urinalysis tests. Blood and urine samples to be obtained before study drug dosing on Day 4. On Day 14, serum chemistry only; subjects with ALT/AST elevations on Day 11 and/or 14 will be followed-up every 5-7 days until resolution.

(i) HBsAg, anti-HCV, anti-HIV, Anti-HBsAb, HBeAg, anti-HBeAb, anti-HBcAb, EBV VCA IgG, EBV VCA IgM, Anti-CMV IgG, and Anti-CMV IgM. HBsAg, anti-HCV, and anti-HIV test results will be collected for all subjects. The results for Anti-HBsAb, HBeAg, anti-HBeAb, anti-HBcAb, EBV VCA IgG, EBV VCA IgM, Anti-CMV IgG, and Anti-CMV IgM tests performed at Screening will be recorded in the (e)CRF for randomized subjects only.

(j) Women of childbearing potential.

(k) Study drug will be administered on Day 1 and Day 10 with 240 mL of water after a fast of at least 8 hours. On Day 1 and Day 10, subjects will also continue to fast for an additional 4 hours after dosing and subjects may consume water ad libitum with the exception of 1 hour before and 1 hour after drug administration. For Days 4 to 9, fasting is not required for dosing.

(l) TAK-536 plasma PK: 6 mL blood samples will be collected on Day 1 at Predose (up to 15 minutes prior to dose [0 hour]) and at 0.5, 1, 2, 3, 4, 6, 8, 12, 16, 24, 36, 48, and 72 hours postdose. On Days 7, 8, and 9 at predose (up to 15 minutes prior to dose [0 hour]) and on Day 10 at predose (up to 15 minutes prior to dose [0 hour]) and at 0.5, 1, 2, 3, 4, 6, 8, 12, 16, 24, 36, 48, 72 hours postdose.

(m) TAK-536 urine PK: urine will be collected starting on Day 1 at Predose (-12 to 0 hour) and at 0 to 2, 2 to 4, 4 to 8, 8 to 12, 12 to 24, 24 to 48, and 48 to 72 hours postdose and on Day 10 at 0 to 2, 2 to 4, 4 to 8, 8 to 12, 12 to 24, 24 to 48, and 48 to 72 hours postdose.

(n) PTEs will be collected from the time of the informed consent to immediately prior to dosing on Day 1 of Period 1.

(o) Subjects will be discharged from the clinic after completion of all scheduled procedures and at the investigator's discretion.

5.0 ANALYSIS ENDPOINTS

5.1 Primary Endpoint

Primary endpoints for TAK-536 (the active moiety derived from TAK-491) of this study are as follows:

- Maximum observed concentration (C_{\max}).
- Time of first occurrence of C_{\max} (t_{\max}).
- Area under the concentration-time curve from time 0 to infinity (AUC_{∞}) (single dose only).
- Area under the concentration-time curve from time 0 to 24 hours (AUC_{24}) (multiple dose only)
- Terminal disposition phase half-life ($t_{1/2z}$) (single dose only).

5.2 Additional Endpoints

Additional endpoints for TAK-536 are as follows:

- Area under the concentration-time curve from time 0 to time of last quantifiable concentration (AUC_{last}) (single dose only).
- Terminal disposition phase rate constant (λ_z) (single dose only).
- Observed concentration at the end of a dosing interval (C_{trough}) (multiple dose only).
- Minimum observed concentration during a dosing interval (C_{\min}) (multiple dose only).
- Average concentration during a dosing interval, at steady state ($C_{\text{av,ss}}$) (multiple dose only).
- Amount of drug excreted in urine from time 1 to time 2 ($A_{\text{et1-t2}}$).
- Renal clearance, (CL_R).
- Fraction of administered dose of drug excreted in urine from time 0 to 72 hr ($f_{\text{e0-72}}$) in single dose and time 0 to 24 hours ($f_{\text{e0-24}}$) for multiple dose. Molecular weight adjustment needed from TAK-491 to TAK-536,

5.3 Safety Endpoints

The safety and tolerability endpoints of TAK-491 40 mg and 80 mg for the study will be determined from the primary safety variables that will include: physical examination findings, vital signs, 12-lead electrocardiogram (ECG) results, laboratory evaluations (hematology, serum chemistry, and urinalysis), and adverse events (AEs).

6.0 DETERMINATION OF SAMPLE SIZE

Total sample size of 64 subjects will be enrolled in this study. Sixteen subjects, 8 per regimen (TAK-491 40 mg and 80 mg), will be randomized to the open-label part of the study. Forty-eight subjects, 16 per regimen (TAK-491 40 mg, 80 mg and placebo), will be randomized to the double-blind part of the study. The sample size is considered sufficient for evaluation of safety, tolerability and PK of each part of the study, and was not based on statistical analysis power considerations.

7.0 METHODS OF ANALYSIS AND PRESENTATION

7.1 General Principles

7.1.1 Summary Statistics and Precision

All tabulations of analysis results will include summaries by following regimens: TAK-491 40 mg (open-label), TAK-491 80 mg (open-label), TAK-491 40 mg (double-blind), TAK-491 80 mg (double-blind) and placebo (double-blind).

No formal statistical test will be performed in this study. Summaries will be based on descriptive analysis.

Means and medians will be presented to 1 more decimal place than the recorded data. The standard deviations (SDs) will be presented to 2 more decimal places than the recorded data. Exceptions may be made for derived data in the database where decimal precision is beyond necessary.

Where appropriate, variables will be summarized descriptively by study visit. For the categorical variables, the count and proportions of each possible value will be tabulated by regimen.

Percentages will be reported to 1 decimal place. For continuous variables, the number of subjects with non-missing values, mean, median, SD, minimum, and maximum values will be tabulated.

The data summaries will be accompanied by individual subjects data listings sorted by study part, regimen, and subject number. All data available from raw data will be listed. The actual day relative to the start of study drug will be determined and included in the listing.

Derived analysis datasets will be produced from raw data. This allows for convenient review of the data as well as any necessary supplemental analyses. All data from the raw data will be included in the derived datasets. Derived dataset specifications will be developed to include the names and definitions of derived variables in the derived SAS datasets. All analyses and data listings will be performed using the derived datasets.

Screen failure subjects will be grouped and listed.

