5.1.2 Secondary Objectives

To evaluate the safety and tolerability of TAK-491 40 mg and 80 mg in healthy Chinese subjects after both single and multiple dose administration.

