6.2 Justification for Study Design, Dose, and Endpoints

This randomized, open-label and double-blind, placebo-controlled, single- and multiple-dose, phase 1 study was designed with the following justification. The parameters listed as primary endpoints are considered appropriate for evaluation of pharmacokinetic profiles associated after single- and multiple-doses, and the additional safety endpoints comprise established safety assessments recognized as reliable, accurate, and relevant.

The pharmacokinetics of TAK-536 after administration of TAK-491 has been thoroughly characterized from data collected during the phase 1 clinical pharmacology program conducted in the United States and Europe. The $t_{1/2z}$ for TAK-536 following TAK-491 administration is approximately 11 hours; the planned sampling scheme after the single dose is approximately 6 half-lives and appropriate. Steady state of TAK-536 is achieved within 5 days of dosing of TAK-491; the multiple-dose duration is appropriate. A total of 64 healthy subjects will be enrolled into the study. An open-label design was used during the dosing of the first 16 subjects (in 2 consecutive cohorts) because the primary outcomes are based on objective measurements, that is, plasma concentrations of TAK-536. Fifteen of these first 16 subjects had a higher ALT and/or AST level on Day 11 than on Day -1. While none of these subjects had Day 11 ALT and/or AST values that exceeded 3×ULN of protocol mandated monitoring criteria (see [Section 7.5](#) [No.1] and [Section 10.2.3](#)), 7 of these exceeded the ULN. None of these ALT/AST elevations were accompanied by symptoms or signs of liver injury or by bilirubin elevation, and resolved without intervention. High frequency of subjects with elevations in ALT and/or AST levels were unexpected and unprecedented, as no similar findings were observed in previous TAK-491 phase 1 through 3 studies with the enrollment of subjects from different races and ethnicities (ie, Caucasians, African Americans, Mexican Americans, Native Americans, Asians, and other ethnicities). While other procedure-related factors, such as high-carbohydrate diet and minimal physical activity during the confinement period in the phase 1 unit, as described in the medical literature [\[10-12\]](#), might have been accountable for these asymptomatic ALT/AST elevations in the present study, a potential drug-related phenomenon has to be definitively ruled out. Hence, a

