double-blind, placebo-controlled study design was adopted to complete the study. A randomization schedule for dose assignment will be used to reduce the potential for selection bias.

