7.11 Safety Analysis

Safety summaries will be based on the Safety Set. All safety assessments, including AEs, clinical laboratory evaluations, 12-lead ECG results, physical examination, and vital signs will be summarized with descriptive statistics by regimen for each part separately and overall, where appropriate, and presented in the data listings.

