7.11.2 Clinical Laboratory Evaluations

Clinical laboratory tests will be evaluated by central laboratory and presented using the International System of Units (SI) units unless otherwise stated. [Table 4.c](#) shows the scheduled measurements for clinical laboratory tests and [Table 7.d](#) shows a list of all clinical laboratory tests.

Table 7.d Clinical Laboratory Tests

Hematology	Serum Chemistry	Urinalysis
Red blood cells	Alanine aminotransferase	pH
White blood cells with differential (neutrophils, eosinophils, basophils, lymphocytes, monocytes)	Albumin	Specific gravity
Hemoglobin	Alkaline phosphatase	Protein
Hematocrit	Aspartate aminotransferase	Glucose
Platelets	Total bilirubin	Blood
	Total protein	Ketones
	Creatinine	Microscopic Analysis (a):
	Blood urea nitrogen	RBC/high power field
	Creatine kinase	WBC/high power field
	γ -Glutamyl transferase	Epithelial cells, casts etc.
	Potassium	
	Sodium	
	Glucose	
	Chloride	
	Triglycerides	
	HDL-C	
	LDL-C	
	Total cholesterol	
Diagnostic Screening:		
Serum	Urine	Breath
HBsAg, anti-HCV, anti-HIV (b) Additional Virology Tests: Anti-HBsAb, HBeAg, anti-HBeAb, anti-HBcAb, EBV VCA IgG, EBV VCA IgM, Anti-CMV IgG, and Anti-CMV IgM (c)	Drug screen, including amphetamines, barbiturates, benzodiazepines, cannabinoids, cocaine, opiates, and cotinine	Breath alcohol test
Female Subjects only:		
Serum hCG at Screening, Check-in, and Study Exit or Early Termination		

EBV= Epstein-Barr virus viral capsid antigen, hCG=human chorionic gonadotropin, RBC=red blood cell, WBC=white blood cell.

(a) Microscopic analysis should be performed only if urine evaluations are abnormal.

(b) HBsAg, anti-HCV, and anti-HIV test results will be collected for all subjects.

(c) The results for the additional virology tests performed at Screening will be recorded in the (e)CRF for randomized subjects only.

The following summaries will be provided for laboratory data by part and regimen:

- Baseline, postdose, and, change from baseline to postdose values for quantitative measurements.
- Number and percent of urine parameters results for categorical measurements.
- Number and percent of subjects with markedly abnormal value (MAV) which identified by the criteria in [Appendix A](#).
- Shift from baseline of high/low/normal values according to normal range criteria (baseline versus each post-baseline visit).

If a subject has multiple values within a particular visit window, the most abnormal result will be used for summary.

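### The placebo-controlled part was added to rule out a drug cause of the ALT/AST rises, but the SAP plans no TAK-491-versus-placebo estimate or interval for ALT or AST and leaves pooling of the laboratory tables unclear

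*SAP*

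**What the plan says.** Protocol 6.2 reports that 15 of the 16 open-label subjects had higher ALT and/or AST on Day 11 than on Day -1, that 7 were above ULN and that none was above 3×ULN. It says that "a potential drug-related phenomenon has to be definitively ruled out" and, for that reason, that a "double-blind, placebo-controlled study design was adopted to complete the study". This is design rationale, not a listed objective. The secondary objective (Protocol 5.1.2) is broader: "To evaluate the safety and tolerability of TAK-491 40 mg and 80 mg in healthy Chinese subjects".

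SAP 7.1.1 sets the analysis policy: "No formal statistical test will be performed in this study. Summaries will be based on descriptive analysis". It lists five table columns, one per part and regimen, with no pooled TAK-491 column.

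For laboratory data, SAP 7.11.2 says: "The following summaries will be provided for laboratory data by part and regimen". The summaries are baseline, postdose and change values, counts of markedly abnormal values (above 3×ULN for ALT and AST, Appendix A), and a table described as "Shift from baseline of high/low/normal values according to normal range criteria", by visit. Protocol 13.1.4 adds a table of out-of-range results. SAP 7.11.5 adds a listing of liver function data.

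On pooling, SAP 7.11 says that safety data are "summarized with descriptive statistics by regimen for each part separately and overall, where appropriate", without saying what is combined. SAP 7.11.1 names a combined double-blind TAK-491 group for adverse events. SAP 7.11.2 names none for laboratory tests.

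**The concern.** Comparison with concurrent placebo is why the design was changed, yet the plan ends with columns side by side. No visit, contrast, baseline rule or measure of precision is fixed for ALT or AST. Any comparison made later would be chosen after the data are seen.

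The main risk is over-reading. If the TAK-491 and placebo columns look alike, a reader who has Protocol 6.2 in mind may conclude that a drug cause has been excluded, with nothing in the tables to show how large an excess remains possible. The only liver threshold that the SAP sets for itself, above 3×ULN, would have counted none of the 16 open-label subjects on Day 11.

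The pooling question affects precision, because 32 against 16 subjects gives narrower intervals than 16 against 16. Two programmers could reasonably build different laboratory tables from the present text.

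**Working it through.** **Inputs from the documents.** Open-label: 7 of 16 above ULN (Protocol 6.2). Double-blind: 16 per arm (Protocol 13.3, SAP 6.0), so 32 against 16 if doses are pooled. The stated total reproduces: 2×8 + 3×16 = 64. It was not based on power, so there is no alpha, effect size or margin to check.

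**Assumptions.** The documents give no placebo rate, and the open-label rate predates the diet change in Amendment 4. Equal observed rates in both arms are therefore assumed and varied. No SD for log ALT or log AST is given; a residual SD of 0.3 to 0.5 is assumed.

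**Step 1: open-label rate.** 7/16 = 43.75%; exact (Clopper-Pearson) 95% CI 19.8% to 70.1%.

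**Step 2: interval for a difference in proportions above ULN.** Newcombe's method, with d = p1 − p2 and Wilson limits (l, u) for each arm:

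- lower = d − √[(p1 − l1)² + (u2 − p2)²]
- upper = d + √[(u1 − p1)² + (p2 − l2)²]

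For 14/32 against 7/16 the Wilson limits are 0.282 to 0.607 and 0.231 to 0.668. With d = 0:

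- lower = −√[(0.4375 − 0.282)² + (0.668 − 0.4375)²] = −0.278
- upper = √[(0.607 − 0.4375)² + (0.4375 − 0.231)²] = 0.267

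| Observed rate in both arms | Pooled v placebo (32 v 16) | One dose v placebo (16 v 16) |
|---|---|---|
| 43.75% | −27.8 to +26.7 points | ±31.0 |
| 25% | −27.2 to +22.6 | ±28.6 |
| 12.5% | −24.7 to +18.0 | ±25.2 |
| 6.25% | −22.5 to +14.8 | not computed |

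**Step 3: effect of a baseline restriction.** Exclusion criterion 17 bars only ALT or AST above 1.5×ULN, so some subjects may enter already above ULN. If 2 of 16 per arm are set aside (assumption; 28 v 14), 12/28 v 6/14 gives −29.5 to +28.1 points and 4/28 v 2/14 gives −27.1 to +20.0.

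**Step 4: would an interval ever be informative?** If the open-label rate recurs on TAK-491 (14/32):

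- placebo 1/16: +37.5 points (+10.5 to +55.2)
- placebo 3/16: +25.0 (−3.8 to +45.8)
- placebo 4/16: +18.8 (−10.3 to +41.2)

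It separates the arms when the placebo rate is low, but not in the other two cases.

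**Step 5: ratio scale.** With three arms and one baseline covariate, df = 48 − 3 − 1 = 44 and t = 2.015. The 95% CI is the estimated ratio divided and multiplied by exp[t × SD × √(1/n1 + 1/16)]. For n1 = 32 the square root is 0.306, and for SD 0.3, 0.4 and 0.5 the factors are 1.20, 1.28 and 1.36. For n1 = 16 it is 0.354, and the factors are 1.24, 1.33 and 1.43.

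**The case against.** The strongest reply is that the SAP breaks no promise. Excluding a drug cause is rationale, not an objective or endpoint. Protocol 13.1.4 commits only to descriptive statistics, and descriptive safety reporting is normal in phase 1. The shift tables already give counts above ULN by arm, so a reader could add the two doses and compute an interval. Protocol 11.0 also provides for an external hepatologist and an independent statistician to review unblinded aggregate data. Much of this stands: the data will be there, and the absence of a test is not a fault. What remains missing is advance commitment to one contrast with its precision. Shift tables cannot supply a baseline-adjusted ratio, and neither Protocol 11.0 nor SAP 7.12 states a comparison.

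On pooling, SAP 7.1.1 and 7.11.2 read alone imply no pooled column. That is fair. The doubt comes from the undefined overall summary in SAP 7.11 and from the pooled group named for adverse events only.

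The proposed contrast can also be criticised. Day 11 alone would miss rises first seen on Day 14, pooling could dilute an effect confined to 80 mg, and a scheduled-value rule is less conservative than the one in SAP 7.11.2: "If a subject has multiple values within a particular visit window, the most abnormal result will be used for summary". These points are met by making the contrast an addition: the shift, Day 14 and most-abnormal tables stay, and each dose is still compared with placebo. Finally, the SAP was signed on 1 and 2 May 2017 and the documents do not show whether unblinding had occurred, so the fix counts as pre-specification only if it had not.

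**Conclusion.** The concern holds and should be fixed. Followed as written, the plan leaves the question that caused the redesign without an estimate or a statement of precision. Equal observed rates above ULN would leave an excess of about 15 to 27 points on pooled TAK-491 unexcluded for common rates of 6% to 44%, and 25 to 31 points for a single dose at rates of 12.5% to 44%. These sizes rest on assumed equal rates. The log-scale factors (1.20 to 1.36 pooled) rest on an assumed SD. The omission itself depends on neither. No analysis of 32 against 16 subjects can be expected to deliver definitive exclusion, but an interval would show what has and has not been excluded.

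**What to change.** In SAP 7.11.2, before unblinding, add for the double-blind part only, as estimation without a test and as a stated exception to 7.1.1:

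- **Main contrast:** pooled TAK-491 against placebo at the scheduled Day 11 visit, with each dose against placebo as supportive.
- **Estimates:** (1) the baseline-adjusted ratio for log ALT and for log AST with 95% CI; (2) the difference, with 95% CI, in the proportion with ALT and/or AST above ULN at Day 11 among subjects with both enzymes at or below ULN at baseline, as defined in SAP 7.1.3.
- **Data rule:** use the scheduled Day 11 value for this contrast, as a stated exception to the most-abnormal-value rule, and report the number without a Day 11 value in each arm.
- **Pooling:** state that laboratory tables carry a pooled double-blind TAK-491 column, as for adverse events.
- **Conclusion:** word it in the SAP and study report as an estimate against concurrent placebo with its interval.

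The cost is wording in SAP 7.1.1 and 7.11.2 and a few tables, with no new subjects or data. The downside is wide intervals and a more modest claim. The phrase in Protocol 6.2 should be softened as well. Because protocol changes need ethics approval (Protocol Appendix B, item 5), that can wait for the next amendment.
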